## 2 OBJECTIVES

The primary objectives of this study are to assess the safety and tolerability of two regimens of UB-311, and to evaluate the immunogenicity of two regimens of UB-311 through measurement of anti-A $\beta$  antibodies.

The secondary objectives are to evaluate the effects of UB-311 on the changes of cognitive and functional performance over a period of 78 weeks, and to investigate whether UB-311 treatment results in changes in amyloid deposition *in vivo* by 18F-AV-45 PET imaging.

## 3 TRIAL DESIGN

This is a 78-week, randomized, double-blind, placebo-controlled, three-arm parallel-group, multicenter Phase IIa trial.

Individuals who were enrolled in the Phase I trial will be excluded from the Phase IIa trial.

### 3.1 Description of the Protocol

The study comprises 3 periods as shown in Table 3.1 (please also see 8.2 Events and Time Schedule):

- An up to 6-week screening period to complete first and second stage screenings,
- A 60-week double-blind randomized treatment period, which includes 2 different UB-311 dosing regimen arms and 1 placebo arm, and
- An 18-week follow-up period.

**Table 3.1 Clinical Schematic Diagram**

	Screening		Treatment											Follow-up	
Visit	S1	S2	V1	V2	V3	V4	V5	V6	V7	V8	V9	V10	V11	V12	V13
Week	-6	~ 0	0	4	12	16	24	28	36	40	48	52	60	64	78
Treatment arms															
Arm 1			↑	↑	↑		↑		↑		↑		↑		
Arm 2			↑	↑	↑		↑p		↑		↑p		↑		
Arm 3			↑p	↑p	↑p		↑p		↑p		↑p		↑p		

↑ : UB-311    ↑ p: placebo

#### 3.1.1 Screening Period

Subjects with probable Alzheimer’s disease based on National Institute of Neurological and Communicative Disorders and Stroke, and Alzheimer’s Disease and Related Disorders Association (NINCDS-ADRDA) Criteria and National Institute on Aging–Alzheimer’s Association (NIA-AA) guidelines are screened at the first stage screening (S1, Weeks -6~0). All laboratory tests required

for evaluating the eligibility of the subjects are performed at S1.

Subjects meeting inclusion criteria 1 to 14 and none of the exclusion criteria are eligible for the second stage screening (S2, Weeks -6~<0) for the positive of  $\beta$  amyloid ( $A\beta$ ) plaques on 18F-AV-45 PET by an imaging expert per central independent review (See Section 3 of Appendix 1 Imaging Protocol).

### 3.1.2 Treatment Period

Subjects meeting all inclusion criteria, presenting no exclusion criteria, and with  $A\beta$  imaging in the brain enter the treatment period, from V1 (Week 0) to V11 (Week 60). These subjects are randomized into one of the 3 treatment arms before treatment initiation at V1.

### 3.1.3 Follow-up Period

The follow-up period comprises 2 visits: V12 (Week 64) and V13 (Week 78).

## 3.2 Endpoints

### 3.2.1 Primary

The primary endpoints of this study are:

- Safety and tolerability of UB-311 during the study period.
- The immunogenicity of UB-311 as measured by
  - Change from baseline in anti- $A\beta$  antibody levels through the end of the study
  - Response rate (see section 6.1.2 for definition)

### 3.2.2 Secondary

The secondary endpoints are:

- The change from baseline in cognitive, functional, and global assessments through the end of the study, including:
  - Alzheimer's Disease Assessment Scale-Cognitive Subscale (ADAS-Cog)
  - Mini-Mental State Exam (MMSE)
  - Alzheimer's Disease Cooperative Study-Activities of Daily Living (ADCS-ADL)
  - Clinical Dementia Rating-Sum of Boxes (CDR-SB)
  - Neuropsychiatric Inventory (NPI)
- The change of amyloid burden from baseline to Weeks 52 and 78 in retention of 18F-AV-45, determined by mean standard uptake value ratio (SUVR) of selected regions of interests (ROIs), such as frontal, temporal, parietal, occipital, and precuneus.

### **3.3 Description of Blinding Methods**

The UB-311 and placebo vials are indistinguishable by appearance. Each treatment box is labeled with a number, which is generated by a computer program from UNS's delegate CRO. Investigators do not have access to the randomization code except under circumstances described in section 6.4.

To maintain the blind during the trial, neither the investigator nor the sponsor will have access to the data that could potentially compromise study blindness during the study.

### **3.4 Description of Randomization**

The list of randomized numbers of treatment kits is generated centrally by UNS's delegate CRO. UB-311 and/or placebo are packaged in accordance with this list.

UNS's delegate CRO provides a list of the randomized treatment box number and a randomization scheme to the Interactive Voice or Web Response System (IVRS/IWRS). The IVRS/IWRS generates the subject randomization list to allocate the treatments to subjects.

Subjects are randomized to one of the three arms in 1:1:1 ratio, providing a projected equal distribution of subjects among groups.

### **3.5 Stopping Rules**

The scientific measures of treatment that correspond to early termination are safety.

In the event of an unexpected and suspected SAE that results in a life-threatening condition or death, the principal investigator(s) will assess the relationship between SAE and the study drug according to the subject's clinical symptoms, clinical data, characteristics of the study medicine and safety endpoints, such as MRI results. If the causality assessment confirms that the SAE is definitely related to the study drug, and the committees of the Data and Safety Monitoring Board (DSMB), the Institutional Review Board (IRB) and Department of Health (DOH) express consensus opinions, the clinical trial might be stopped. The subject will receive immediate clinical treatment for the adverse event and will not receive additional administrations of the study medicine.

After this trial ends, all attempts should be made to follow up all subjects through telephone calls or by direct contact, in order to document any delayed or unresolved adverse drug reactions or adverse events.

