### 5.2 Dosing Regimens and Rationale

Eligible subjects are randomly assigned in 1:1:1 ratio to one of the following treatments:

- Arm 1: UB-311 for a total of 7 intramuscular (IM) injections at Weeks 0, 4, 12, 24, 36, 48, and 60.
- Arm 2: UB-311 for a total of 5 IM injections at Weeks 0, 4, 12, 36, and 60. In order to maintain the blindness, subjects assigned to arm 2 will receive 2 IM injections of placebo at Weeks 24 and 48.
- Arm 3: placebo for a total of 7 IM injections at Weeks 0, 4, 12, 24, 36, 48, and 60.

Injections will be given on alternate arms or at different sites, which will be recorded.

The 300 µg of UB-311 in 0.5 mL sterile aqueous solution is the maximal concentration feasible in the current intramuscular injection formulation containing CpG-ODN and Adjuvphos. Therefore, the dose escalation in the Phase IIa study will be based on the cumulative doses according to various treatment schedules instead of different amount of UB-311 per injection.

A total of three injections of UB-311 at Weeks 0, 4, and 12 with a cumulative dose of 900 µg were evaluated in the Phase I clinical trial that showed acceptable safety, tolerability, immunogenicity, and positive clinical outcome in mild to moderate AD patients over a one-year period. In the Phase IIa study, the dose will be escalated based on increased number of injections than the Phase I study. Subjects assigned to Arm 1 will receive 7 injections of UB-311, 300 µg each at Weeks 0, 4, 12, 24, 36, 48, and 60 with a cumulative dose of 2,100 µg. Subjects assigned to Arm 2 will receive 5 injections of UB-311, 300 µg each at Weeks 0, 4, 12, 36, and 60 with a cumulative dose of 1,500 µg.

The Phase I study showed that three priming doses at Weeks 0, 4, and 12 successfully established sufficient immunogenicity against Aβ, thus the priming schedule was adopted for the current study. Additional doses for Arm 1 and Arm 2 at the frequency of 3 and 6 months, respectively, are intended to assess the requirement for maintaining elicited antibody levels. Furthermore, the dosing regimen of Arm 1 represents the most frequent injection schedule, allowing evaluation of safety and efficacy of the strongest antibody response.

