**Activities of Daily Living (ADL):**

\*Instrumental ADL refers to preparing meals, shopping for groceries or clothes, using the telephone, managing money, etc.

\*\*Self care ADL refers to bathing, dressing and undressing, feeding self, using the toilet, taking medications, and not bedridden.

The investigator makes a judgment regarding whether or not the AE is related to study drug, using the definitions below. The investigator is to evaluate any changes in laboratory values and make a determination as to whether or not the change is clinically important and whether or not the changes are related to study drug. However, even if the investigator determines there is no relationship to the study drug, the AE or clinically significant laboratory abnormality must still be recorded in the CRF along with the investigator’s assessment of relationship as follows:

Relationship	Description
Unrelated	The AE must definitely have been caused by the subject’s clinical state, or the study procedure/conditions (i.e. it had no association with the study drug)
Unlikely	The temporal association between the AE and the study drug was such that the study drug was not likely to have any reasonable association with AE.
Possible	The AE followed a reasonable temporal sequence from the time of drug administration, but could have been produced by the subject’s clinical state or the study procedures / conditions.
Probable	The AE followed a reasonable temporal sequence from the time of study drug administration, abated upon discontinuation of the study drug and could not be reasonably explained by the known characteristics of the subject’s clinical state.
Definite	The AE followed a reasonable temporal sequence from the time of study drug administration, abated upon discontinuation of the study drug and reappeared when the study drug is introduced.

It is usually important for the investigators to take information of underlying diseases, concomitant drugs, temporal relationship of the onset of the event to the time of dosing the study medication, and re-challenging outcomes, into account when making a causal relation decision.

It is the investigators' responsibility to follow proactively the outcome of each AE/SAE until resolution or stabilization of the condition or lost of follow-up.

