### **7.9 Data and Safety Monitoring Board**

A Data and Safety Monitoring Board (DSMB) with members independent from the sponsor and the clinical investigators is implemented in order to ensure the protection and safety of enrolled patients in the study. The DSMB members include:

- An expert in the clinical aspects of the Alzheimer’s disease patient population being studied,
- A biostatistician, and
- An investigator with expertise in current clinical trials conduct and methodology.

Each DSMB member will sign a Conflict of Interest Statement at the time they are invited to participate to declare that he/she does not have financial, proprietary, professional, or other interests that may affect impartial, independent decision-making by the DSMB.

The DSMB is responsible for reviewing safety data, study conduct, and progress. Based on the review, the DSMB makes recommendations to the clinical investigators concerning the continuation, modification, or termination of the trial. In the V203-AD trial, the DSMB will convene for the first time after the 9th subject completes Visit 6, for the second time after the 18th subject completes Visit 10, and for the third time after the 27th subject completes V13 to assess the safety data in the V203-AD trial. An emergency meeting of the DSMB may be called at any time by the DSMB Chair should questions on participants’ safety or other unanticipated problems arise.

It is the responsibility of CRO or sponsor to ensure that the DSMB is informed about safety information relevant to the study. This includes providing the DSMB with preclinical data, results from the phase I study, and the phase IIa protocol before initiation of the trial, and a DSMB report at least one week prior to a scheduled meeting. The CRO is responsible for preparing the DSMB briefing materials, which consist of:

- Subject recruitment, retention, and withdrawal information
- AEs and SAEs
  - Tabulated by preferred term, intensity, seriousness, duration, treatment given, and the relationship to the study drug and study procedure
  - Individual events of particular concern
- Tabulated clinical test results and laboratory values (e.g. raw values, changes/shifts from baseline, and clinical abnormalities), including clinical chemistry, hematology tests, and 12-lead electrocardiogram (ECG)
- Vital signs and physical exam outcomes

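### Under the protocol's own causality scale, a first-occurrence fatal or life-threatening SAE cannot be graded 'Definite', so the stopping condition in section 3.5 is effectively out of reach

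*Protocol*

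**What the plan says.** Protocol 3.5 (Stopping Rules) is triggered by an unexpected, suspected SAE that kills the subject or threatens life. The principal investigators assess causality from the subject's "clinical symptoms, clinical data, characteristics of the study medicine and safety endpoints, such as MRI results". The trial may then be stopped "If the causality assessment confirms that the SAE is definitely related to the study drug" and the DSMB, IRB and DOH agree. The affected subject "will not receive additional administrations of the study medicine".

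Protocol 7.6 gives the causality scale for all adverse events: Unrelated, Unlikely, Possible, Probable, Definite. It introduces the scale with "The investigator makes a judgment regarding whether or not the AE is related to study drug, using the definitions below". All of the top three levels need a reasonable time sequence after dosing. 'Probable' adds that the event "abated upon discontinuation of the study drug and could not be reasonably explained" by the subject's clinical state. 'Definite' requires that it "abated upon discontinuation of the study drug and reappeared when the study drug is introduced".

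Neither document gives another causality scale or another meaning for a definite relationship. The SAP tabulates TEAEs by causal relationship (5.12.2) without redefining the levels, and plans no interim analysis (5.14).

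**The concern.** The rule asks for a grade that depends on two observations: that the event went away when the drug was withdrawn, and that it returned when the drug was given again. A death rules out both. For a survivor, the rule itself prevents the second by ending that subject's dosing. Read with the protocol's own definitions, the condition therefore excludes first occurrences of the events it was written for.

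This is the only trial-level stopping criterion stated in advance. Protocol 7.10 takes the risk seriously: it builds its safeguards on the meningoencephalitis reported in over 6% of patients given an earlier Aβ vaccine. If a subject died, one party could apply 7.6 literally and find the condition unmet, while another applied general clinical judgment and found it met. The protocol gives the investigators, DSMB, IRB and DOH no agreed way to settle that.

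**Working it through.** The plan gives no figure to reproduce. The check sets the definitions in 7.6 against the events in 3.5.

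**What each level requires (7.6)**

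| Level | Abated on discontinuation | Reappeared on re-exposure |
|---|---|---|
| 3 Possible | not required | not required |
| 4 Probable | required | not required |
| 5 Definite | required | required |

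**What each event in 3.5 can show**

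| Event | Can abate? | Can reappear? | Highest level |
|---|---|---|---|
| First-occurrence death | no | no | 3 of 5 |
| First-occurrence life-threatening event, subject survives | yes | no, dosing ends under 3.5 | 4 of 5 |
| Milder reaction that resolved, then returned as a fatal or life-threatening event after a later dose | yes (the earlier episode) | yes | 5 of 5 |

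Section 3.5 requires level 5, so only the last row can meet it.

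Level 3 for a death is an upper bound. 'Possible' also expects that the subject's clinical state or the study procedures could have caused the event. A death with plausible timing and no such alternative explanation does not fit 'Possible' either, and on a strict reading has no grade.

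**How far the exception extends**

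A recurrence needs an earlier UB-311 dose, so it can arise only after the second or a later UB-311 injection (schedule in 5.2).

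- Arm 1: 7 UB-311 injections, at Weeks 0, 4, 12, 24, 36, 48 and 60. Doses 2 to 7 qualify: 7 − 1 = 6 of 7.
- Arm 2: "UB-311 for a total of 5 IM injections at Weeks 0, 4, 12, 36, and 60". Doses 2 to 5 qualify: 5 − 1 = 4 of 5.

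In either arm, an event that first appears after the Week 60 dose cannot recur on treatment, because no dose follows. These counts show where the exception is possible, not how likely it is. The documents give no rate for such events, so no probability of meeting the condition is claimed.

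**The case against.** The strongest objection is that 3.5 never cites 7.6. It names its own assessors and its own evidence and does not use the grade label 'Definite'. Section 7.6 itself rests causality on the investigator's clinical judgment and treats rechallenge as one of several factors to weigh. Elsewhere the protocol describes relatedness in phrases that are not grades on the scale (7.7, 7.8, 9.4.2). The wording in 3.5 could be plain language of the same kind, and the gap in 'Possible' noted above suggests the table was meant as guidance.

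Part of this stands: the link to 7.6 is an inference. But 7.6 goes on to say that the judgment is made with its definitions, and it covers every AE and SAE. The evidence list in 3.5 says what to look at, not what makes a relationship definite. If another standard was meant, it is unwritten, and the clarification is still needed.

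The second objection is that little depends on the grade. Stopping under 3.5 is optional and also needs three bodies to agree. The DSMB can recommend termination with no grade at all, and "An emergency meeting of the DSMB may be called at any time by the DSMB Chair" (7.9); 7.10 also provides for meetings on urgent safety events. All of this stands and limits the consequence. It does not repair the rule: 7.9 and 7.10 state no stopping criterion, and the option in 3.5 opens only once its condition is met.

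Third, 3.5 is not limited to first occurrences, and in a repeat-dose trial reactions can recur. That is correct, and the conclusion is limited accordingly.

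**Conclusion.** The concern holds. If the 7.6 definitions govern 3.5, a first-occurrence fatal SAE falls at least two levels short of the required grade (3 against 5) and a first-occurrence life-threatening SAE at least one level short (4 against 5). Only a recurrence after an earlier, milder episode that resolved can meet the condition.

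This rests on two assumptions: that 7.6 is the scale behind the wording in 3.5, which the protocol does not state, and that its definitions are applied as written. The defect lies in the written trigger and not in safety oversight as a whole, because the DSMB route remains open. It should be fixed, but it does not undermine the design.

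**What to change.** Reconcile 3.5 with 7.6. State in 3.5 whether the 7.6 scale applies, and align the wording so that the fatal and life-threatening events named there are capable of meeting the stated condition. The reconciliation has to cover 'Probable' as well as 'Definite', since both require abatement, which a death cannot show. Carry the result into the DSMB text in 7.9. Which causality level or stopping criterion should apply is for the sponsor's clinical team and the DSMB to decide.

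The cost is a wording amendment to the protocol, with no new data, visits or patients.

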## 4 SELECTION AND WITHDRAWAL OF SUBJECTS

### 4.1 Number of Subjects

It is planned to recruit approximately 45 subjects (15 per arm) to receive study treatment in the 78-week double-blind, placebo-controlled study. The randomization procedure continues until the target number of treated patients is reached.

The screen failure rate is estimated to be 50%; therefore, to reach this number it is planned to screen at least 90 subjects.

### 4.2 Inclusion Criteria

For inclusion in the study subjects must fulfil all of the following criteria:

1. Male or female aged between 60-90 years old.
2. Probable Alzheimer's disease based on the National Institute of Neurological and Communicative Disorders and Stroke and the Alzheimer's Disease and Related Disorders Association (NINCDS-ADRDA) criteria and National Institute on Aging-Alzheimer's Association (NIA-AA) guidelines.
3. Mini-Mental State Examination (MMSE) scores between 20 and 26 (inclusive).
4. Clinical dementia rating (CDR) scores of 0.5 or 1.
5. At least 6 years of education or sufficient work history (to exclude mental retardation).
6. Visual and auditory acuity adequate for neuropsychological testing.
7. Stable doses of permitted medications for 3 months before screening, such as acetyl cholinesterase (AChE) inhibitors, N-methyl-D-aspartate (NMDA) receptor antagonist, ergot alkaloids or their derivatives for cognitive enhancement.
8. Hachinski ischemic score (HIS)  $\leq 4$  (original score).
9. Geriatric Depression Scale-Short Form (GDS-SF)  $< 6$ .
10. Eastern Cooperative Oncology Group (ECOG) performance status 0-2.
11. Female must either be post-menopausal (no menstrual period for  $> 1$  year), surgically sterilized or agree to avoid becoming pregnant during the entire period of this study; while sexually active fertile male must agree to use effective birth control methods throughout the study duration, if their sexual partner(s) are women of childbearing potential.
12. With a caregiver who has frequent contact with the subject (e.g. an average of 10 hours per week or more) and agrees to sign the informed consent form (ICF), to perform study-related AD scales and to accompany or delegate a companion with the subject to all visits. A companion needs not to be a family member (with kinship).
13. Both patient and his/her caregiver should sign the written informed consent before undergoing any study procedures.
14. Agree not to donate blood or blood products for transfusion during the study and for 3 months thereafter.

15. A positive of A $\beta$  plaque on 18F-AV-45 PET by an imaging expert (confirmed during the second stage of screening per central independent review).

### **4.3 Exclusion Criteria**

Any of the following is regarded as a criterion for exclusion from the study:

1. Clinically significant neurological disease other than Alzheimer's disease, such as Parkinson's disease, multi-infarct dementia, Huntington's disease, normal pressure hydrocephalus, brain tumor, progressive supranuclear palsy, seizure disorder, subdural hematoma, multiple sclerosis, or history of significant head trauma followed by persistent neurologic deficits or known structural brain abnormalities.
2. Screening MRI scan with evidence of central nervous system (CNS) infection, cerebrovascular disease, infarction, or other focal lesions, or a single area of superficial siderosis, or a prior macrohemorrhage, or more than four microhemorrhages, multiple lacunes or lacunes in a critical memory structure.
3. Major depressive episode or manic episode as described in Diagnostic and Statistical Manual of Mental Disorders, Fifth Edition (DSM-V) within the past 1 year before screening. Psychotic features, agitation or behavioural problems within the last 3 months before screening which could lead to difficulty in complying with the protocol.
4. History of schizophrenia (DSM-V criteria).
5. Any significant systemic illness or unstable medical condition which could lead to difficulty in complying with the protocol.
6. History of alcohol or substance abuse or dependence within the past 2 years before screening (DSM-V criteria).
7. History of autoimmune disease, including but not limited to ankylosing spondylitis, Sjogren's syndrome, systemic lupus erythematosus, rheumatic arthritis, or multiple sclerosis.
8. History of severe systemic disease that may affect a subject's participation at the investigator's discretion.
9. History of anaphylaxis; other serious adverse reactions to any vaccine; or any serious allergic reactions to medications requiring treatment.
10. Use of any prohibited medications within 4 weeks prior to screening
11. Use of any investigational drug within 4 weeks before screening.
12. Current participation in clinical studies involving ADAS-Cog, MMSE, ADCS-ADL, CDR-SB, or NPI being collected more than one time per score per year.
13. Previous exposure to any anti-A $\beta$  immunotherapy.
14. History of cancer, including solid tumors and hematological malignancies (except basal cell and in situ squamous cell carcinomas of the skin that have been excised and resolved).
15. Received blood or blood derivatives treatment within 3 months prior to screening.

16. Positive serology for hepatitis B virus (HBV), hepatitis C virus (HCV), or human immunodeficiency virus (HIV).
17. Current or recent participation (within 12 months before screening) in any procedures involving radioactive agents such that radiation exposure of the subject in any given year would exceed the whole-body limits of annual and total dose commitment of 5 rems set forth in the US Code of Federal Regulations (CFR) Title 21 section 361.1.
18. Abnormal clinical laboratory values as listed below, and determined to be clinically significant by the investigator at the screening:
  - Serum antinuclear antibody (ANA) >1:80
  - Rheumatoid factor (RF) result is  $\geq 17$  IU/mL
  - Platelets <150,000 or >500,000/mm^3
  - White blood cells (WBC) <3,000 or >10,500/mm^3
  - Absolute neutrophil count (ANC) <1,500/mm^3
  - Prothrombin time (PT) <9 or >13 seconds
  - Activated partial thromboplastin time (aPTT) <26.9 or >36.3 seconds
  - Serum creatinine >2 mg/dL
  - Glycosylated hemoglobin (HbA1c) >8.5%
  - Erythrocyte sedimentation rate (ESR)  $\geq$  age-adjusted upper limit of reference range (ULRR), i.e. over 50 years old: male  $\geq 20$  mm/hr, female  $\geq 30$  mm/hr; over 85 years old: male  $\geq 30$  mm/hr, female  $\geq 42$  mm/hr
  - C-reactive protein (CRP) >0.5 mg/dL
  - Aspartate aminotransferase (AST) >84 U/L
  - Alanine aminotransferase (ALT) >80 U/L

